7.6.4 Transvaginal Ultrasound (for Subjects with an Intact Uterus Only)

A transvaginal ultrasound (TVU) will be conducted to assess the uterus and adnexa. Images obtained will also be used to determine endometrial thickness at the central ultrasound laboratory. Date of the TVU will be entered in the eCRF. The TVU must be performed by a trained study staff member and images must be sent to a central reader. The results of the TVU at Visit 1 (Screening), including centrally-determined endometrial

thickness, will be used to assess eligibility. The subject should not be randomized until the centrally read TVU result indicates the endometrial thickness (double-layer) is <4 mm.

If at Screening, the locally read endometrial thickness is evidently, according to the Investigators judgment, more than 4 mm, the subject would not be eligible for the study and the images from the TVU should not be sent to the central ultrasound laboratory.

At 12 weeks (Visit 5), the TVU will be performed and the endometrial thickness (double-layer) will be determined by a central reader following the same procedure. If the subject leaves the study before Week 12, the TVU should be performed as part of the early termination visit.

Any symptomatic and/or large fibroids (estimated size >3 cm) or uterine polyps observed in the TVU at Screening (Visit 1) will exclude the subject from the study. Subjects with endometrial polyps identified during the study period will be discontinued, endometrial polyps should be reported as an AE, and the AE should be captured as the reason for discontinuation.

Detailed procedures will be specified in a separate document. Details about the central ultrasound laboratory are provided in Section 10.1.

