9.2 Determination of Sample Size

Approximately 600 subjects, about 300 subjects per arm (1:1 randomization ratio), will be randomized in the study.

Table 9.2-1 shows the difference between ospemifene and placebo and the effect size in each of 4 co-primary endpoints, namely vaginal pH, percentage of parabasal cells and percentage of superficial cells in the maturation index of the vaginal smear, and MBS of vaginal dryness for the two pivotal studies.

Table 9.2-1 Change from Baseline to Week12 in Two Pivotal Studies

| Primary Efficacy Variable | Study | Ospemifene | Placebo | Difference | SDcommon | Effect Size ^{*2)} |
|---------------------------|----------|-------------|---------|------------|----------|----------------------------|
| MBS of Vaginal Dryness | 15-50310 | C P I | | | | |
| | 15-50821 | | | | | |
| Vaginal pH | 15-50310 | | | | | |
| | 15-50821 | | | | | |
| % Parabasal Cells | 15-50310 | | | | | |
| | 15-50821 | | | | | |
| % Superficial Cells | 15-50310 | | | | | |
| | 15-50821 | | | | | |

*1) Mean±SD

*2) Effect size = $\frac{\text{Difference}}{\text{SDcommon}}$; SDcommon = $\sqrt{\text{SD}_{\text{Ospemifene}}^2 + \text{SD}_{\text{Placebo}}^2}$

For the planned study, referring to the results in

Table 9.2-1, the effect size is assumed to be 0.27 for MBS of vaginal dryness, 0.70 for vaginal pH, 0.83 for % parabasal cells and 0.68 for % superficial cells. Table 9.2-2 shows the power of two-sided t-test with significance level of 0.05 and total sample size of 600 (300 for each treatment group) for each of the 4 co-primary endpoints under the assumed effect size. A sample size of 600 patients provides $\geq 90\%$ power to assess the 4 co-primary efficacy endpoints.

Table 9.2-2 Expected Power with Total Sample Size of 600

| | MBS of Vaginal Dryness | Vaginal pH | % Parabasal Cells | % Superficial Cells | 4 Co-Primary Endpoints |
|-------------|------------------------|------------|-------------------|---------------------|------------------------|
| Effect Size | | | | | C P1 |
| Power | | | | | |

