4.2 Study Blinding and Randomization

After screening, subjects who have $\leq 5\%$ superficial cells in the maturation index of the vaginal smear, a vaginal pH > 5.0 and vaginal dryness as MBS of VVA based on self-assessment, who also meet all other eligibility criteria, will be randomized in a 1:1 ratio to receive either ospemifene 60 mg QD or matching placebo for 12 weeks.

Randomization will be stratified by severity of MBS of vaginal dryness at Visit 2 and by the presence or absence of the uterus. Randomization of subjects without a uterus will be limited to 60% of the study population.

This study will be conducted in a double-blind manner using a placebo matching the test drug in appearance, labeling, and packaging. All subjects, the investigator, all study personnel, and the sponsor will be blinded to the treatment assigned at randomization until database lock.

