10 SAFETY

Safety analyses will be conducted on the Safety Population. For all safety analyses, emphasis will be on characterizing the changes from baseline and flagging clinically relevant abnormal findings, if feasible. If a test or assessment is measured more than once prior to the first dose of study medication, the baseline measurement is the last non-missing value that is observed prior to the first dose of study medication.

To calculate 95% confidence intervals for differences in incidence proportions, FREQ procedure and RISKDIFF option will be used.

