2) Summary of TEAEs and Treatment-related AEs by System Organ Class and Preferred Term

For each treatment group, the number and percentage of subjects who experience TEAE (and Treatment-related AEs) will be counted by SOC and PT for assessments of short and long term safety. The difference in the percentage and its 95% CI will also be calculated. For assessment of short term safety, This analysis will be performed for specific TEAEs for assessment of short term safety, namely

- Breast-related TEAE
- Reproductive system-related TEAE
- Lipid-related TEAE
- Coagulation-related TEAE
- Chemistry-related TEAE

TEAEs and Treatment-related AEs at least 2% in any treatment groups will be analyzed in a similar way.

3) Summary of Serious TEAEs and TEAEs Leading to Withdrawal by System Organ Class and Preferred Term

For each treatment group, the number and percentage of subjects who experience serious TEAE and TEAE leading to withdrawal will be counted by SOC and PT for assessment of short term safety. The difference in the percentage and its 95% CI will also be calculated.

4) Summary of TEAEs and Treatment-related AEs by System Organ Class by Maximum Severity and Outcome

For each treatment group, the number and percentage of subjects who experience TEAE (and treatment-related AEs) will be counted by SOC and PT, and by maximum

severity and outcome for assessment of short term safety. The order of severity and outcome are shown in Table 6.

Table 6 Order of Priority for Counting Number of Subjects

Order of Priority	Severity	Outcome
1	Severe	Fatal
2	Moderate	Recovered/Resolved with sequelae
3	Mild	Not recovered/Not resolved
4		Recovering/Resolving
5		Recovered/Resolved
6		Unknown

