10.4 Endometrial Safety

For subjects with intact uterus, summary tables of endometrial histology and endometrial thickness will be presented at baseline, Week 12 for each treatment group. Change from baseline to Week 12 in endometrial thickness will be summarized for each treatment group.

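### In the SAP 10.1 adverse event tables, terms possible only with a uterus use the whole Safety Population as denominator, so percentages and arm differences are diluted up to 2.5-fold

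*SAP*

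**What the plan says.** SAP 10 sets the population: "Safety analyses will be conducted on the Safety Population". SAP 5 defines it as everyone randomized and dosed, whatever their uterus status. SAP 10.1 item 2 then states: "For each treatment group, the number and percentage of subjects who experience TEAE (and Treatment-related AEs) will be counted by SOC and PT". It adds the arm difference with its 95% CI, repeats the analysis for named groups of events including reproductive-system events, and adds a table with a frequency cut: "TEAEs and Treatment-related AEs at least 2% in any treatment groups will be analyzed in a similar way". Item 3 does the same, with differences and CIs, for serious events and events leading to withdrawal. None of these items mentions a denominator restricted by uterus status.

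On who is enrolled, SAP 4.2 says: "Randomization of subjects without a uterus will be limited to 60% of the study population". Uterus status is also a randomization stratum.

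On which events reach these tables, Protocol 7.6.4 says: "Subjects with endometrial polyps identified during the study period will be discontinued, endometrial polyps should be reported as an AE". Protocol 7.6.5 likewise requires endometrial hyperplasia and endometrial cancer found during the study to be reported as AEs, with the AE recorded as the reason for discontinuation.

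Elsewhere the SAP does restrict the denominator. Section 10.4 says: "For subjects with intact uterus, summary tables of endometrial histology and endometrial thickness will be presented" at baseline and Week 12.

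**The concern.** A woman without a uterus cannot have an endometrial polyp, endometrial hyperplasia or endometrial cancer, and under Protocol 7.6.4 and 7.6.5 she has neither ultrasound nor biopsy. She adds one to the denominator and can never add to the numerator. The SAP applies the at-risk principle to scheduled histology and thickness in 10.4 but does not carry it into the AE tables.

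The AE tables matter because they are the only planned place where these terms get an arm difference and a CI. SAP 10.4 provides neither for histology and names no summary of polyps seen on ultrasound. Safety and tolerability relative to placebo is a primary objective. A reader who takes an absolute percentage, a risk difference or its upper limit from these tables as the risk for a woman with a uterus will take a figure that is too low. The amount depends on the enrolled mix and not on the drug.

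**Working it through.** **Inputs from the documents.** About 300 subjects per arm, 1:1 (Protocol 9.2). At most 60% without a uterus (SAP 4.2). Stratification by uterus status (SAP 4.2). The interval is the 95% CI of the arm difference, from the FREQ procedure with RISKDIFF (SAP 10).

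**Assumptions.** Shares of 30% and 45% without a uterus are illustrative, because only the cap is stated. Event counts are illustrative. All randomized women are dosed and the mix is equal between arms. The SAP does not name the interval type, so Wald is used.

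**Step 1: the plan's own figure.** The documents state no AE rate or AE precision. The only figure to reproduce is the power behind 300 per arm, given as at least 90% for a "two-sided t-test with significance level of 0.05". For dryness, the effect size of 0.27 gives 0.27 x sqrt(300/2) = 3.31, and power is about Phi(3.31 - 1.96) = 0.91. The other three effect sizes (0.70, 0.83, 0.68) each give power above 0.9999, so joint power is about 0.91. The base of 300 per arm is confirmed.

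**Step 2: dilution factor.** With n per arm and a share s without a uterus, n(1 - s) women are at risk. For x events, the planned percentage is x/n and the at-risk percentage is x/[n(1 - s)]. The second divided by the first is 1/(1 - s).

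**Step 3: 3 v 0 events and the 2% cut.** With p = 3/m and no events in the other arm, the Wald upper limit is p + 1.96 x sqrt[p(1 - p)/m]. The smallest count reaching 2% of 300 is 6.

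| Share without uterus | m at risk per arm | Factor | Difference, 3 v 0 (points) | Wald upper limit (points) | 6 events as % of m |
|---|---|---|---|---|---|
| As planned, all 300 | 300 | 1.00 | 1.00 | 2.13 | 2.0 |
| 30% (assumed) | 210 | 1.43 | 1.43 | 3.03 | 2.9 |
| 45% (assumed) | 165 | 1.82 | 1.82 | 3.86 | 3.6 |
| 60% (cap) | 120 | 2.50 | 2.50 | 5.29 | 5.0 |

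At the cap the arithmetic is 0.025 + 1.96 x sqrt(0.025 x 0.975/120) = 0.0529, against 0.010 + 1.96 x sqrt(0.010 x 0.990/300) = 0.0213. The upper limits differ 2.49-fold before rounding.

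**Step 4: other counts at the cap.** For 6 v 1 events the difference is 1.67 points with upper limit 3.38 on 300, and 4.17 points with upper limit 8.39 on 120, a 2.48-fold change in the limit. For 0 v 0 a Wald interval is 0 to 0 on either denominator, so nothing is diluted. Five events in one arm are 5/300 = 1.67%, below the 2% cut, but 5/120 = 4.17% of women at risk.

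**Step 5: ratio between arms.** If the share is equal in both arms, (1 - s) cancels. Six v one is 6:1 on either denominator.

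**The case against.** The strongest reply is that the endometrial question is already handled. A reader might infer from the AE tables that the trial understates endometrial risk as a whole 2.5-fold. The documents do not support that. The stated endometrial objective (secondary Objective 3) concerns histology, and SAP 10.4 tabulates histology and thickness at Week 12 in women with a uterus. This stands, and it confines the point to the AE tables.

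Other limits also stand:

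- Sixty per cent is a ceiling on enrolment and not an expected share.
- Bleeding of undetermined cause is coded as vaginal bleeding (Protocol 7.6.6), which women without a uterus can also have. The factor does not apply to that term.
- Nothing requires endometrial thickening as such to be reported as an AE.
- SAP 13.1 replaces per-arm intervals with the interval for the difference, so no per-arm upper limit is planned that could be understated.
- The 2% table is additional. The full SOC/PT and reproductive-system tables have no cut, and all AEs are listed, so no event is hidden.
- At the cap the 3 v 0 interval includes zero on either denominator (about -0.1 to 2.1, or -0.3 to 5.3 points). The change is one of scale and does not reverse a comparison.

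Three further arguments carry less weight. First, uterus status is tabulated by arm for the ITT Population (SAP 7.2), which has the same entry rule as the Safety Population, so a reader could re-base a percentage. That reader would still have to recompute the difference and its CI. Second, an all-treated percentage is a valid incidence in the treated population. That is a reason to keep the table, but it does not answer the question for women at risk. Third, women with a uterus who stop before Week 12 have no scheduled biopsy and would stay in the restricted denominator. It would therefore be imperfect for histological terms, but the early termination visit includes ultrasound, so polyps can still be found.

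**Conclusion.** The point holds for AE terms possible only with a uterus: chiefly polyps, and hyperplasia and endometrial cancer reported as AEs. In SAP 10.1 items 2 and 3, including the reproductive-system table and the 2% table, their absolute percentages and arm differences are diluted by 1/(1 - share without a uterus). That is 1.43-fold at 30%, 1.82-fold at 45% and at most 2.5-fold at the cap. The limits of the difference are diluted by nearly the same factor when events occur. SAP 10.4 does not fill the gap, because it gives no arm difference, no CI and no stated polyp summary.

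The conclusion rests on reading the whole-population denominator from SAP 10 and 10.1. No text names a denominator for these terms, and the table mock-ups are a separate document not available here. The long-term tables cover only women who continued into Part B. Their uterus mix is not stated or separately capped, so the factor there could differ. No primary efficacy result is affected. The change is worth making because the reported absolute risks would otherwise mislead and the correction is cheap.

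**What to change.** In SAP 10.1, fix before unblinding a list of preferred terms that can occur only in women with a uterus. For those terms, in items 2 and 3, use Safety Population subjects with an intact uterus in each arm as the denominator for the percentage, the difference, its 95% CI and the 2% cut. Print that denominator in the column header and keep the all-subject table alongside. Leave vaginal bleeding off the list.

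The cost is a few lines of SAP text, a short term list and one extra table. No new data are needed, since uterus status is a randomization stratum and a recorded baseline characteristic (Protocol 7.2). The downside is that the figures for these terms will look less favourable.

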10.2 Vital Signs

Summary statistics of observations (blood pressure, pulse rate, and oral temperature) and its change from baseline to each scheduled visit (Weeks 4, 8, and 12) will be calculated by treatment group.

10.3 Laboratory Evaluations

Safety laboratory tests shown in Table 7 will be conducted at screening, randomization, Week 12, and early termination before Visit 5 (hereafter ET).

Table 7 Safety Laboratory Tests

Category	Evaluation Items
Hematology Tests	hematocrit, hemoglobin, platelet count, red blood cell (RBC) count, white blood cell (WBC) count with differential (eosinophil count, basophil count, neutrophil count, monocyte count, lymphocyte count), platelet count, mean corpuscular hemoglobin (MCH), mean corpuscular hemoglobin concentration (MCHC), mean corpuscular volume (MCV), RBC distribution width (RDW), mean platelet volume (MPV)
Blood Chemistry Tests	ALP, ALT, AST, total bilirubin, GGT, LDH, BUN, creatinine, uric acid, sodium (Na), potassium (K), chloride (Cl), calcium (Ca), glucose, total protein
Lipids	Total cholesterol, low-density lipoprotein (LDL) cholesterol, very-low-density lipoprotein (VLDL) cholesterol, high-density lipoprotein (HDL) cholesterol, and triglycerides
Coagulation	Thromboplastin time, fibrinogen, antithrombin III, , protein-C, and protein-S
Urinalysis for Quantitative	pH, specific gravity
Urinalysis for Qualitative	Color, bilirubin, glucose, ketones, nitrite, occult blood, protein, microscopic evaluation of sediment, and urobilinogen

ALT = alanine aminotransferase; AST = aspartate aminotransferase; ALP = alkaline phosphatase; GGT = gamma-glutamyl transferase; LDH, lactate dehydrogenase; BUN, blood urea nitrogen

The measurements on safety laboratory evaluations will be handled as follows:

- 1) For quantitative scale items, summary statistics of measurements taken at baseline, Week 12 will be calculated by treatment group. The change from baseline to Week 12 will be also calculated by treatment group.
- 2) For qualitative scale items, frequencies for each category at baseline, Week 12 will be counted by treatment group.
- 3) For all laboratory analytes in Appendix 3, proportion of subjects who meet the predefined limits at any timepoints will be calculated. Difference in the incidence proportion among treatments and its 95% CI will be calculated. This analysis will be performed using data until Visit 5. The analysis will be applied to data taken at the last timepoint before stopping dosing until Visit 5.

The factor V Leiden will not be summarized.

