8.5 Early Termination Procedures

If a subject discontinues from the study early (i.e., before end of treatment period Visit 5), the following measurements and/or evaluations will be made and recorded in the eCRF:

- Record concomitant therapy
- Assess for AEs
- Assess symptoms of VVA
- Assess FSFI
- Assess UDI-6

- Measure vital signs (BP, pulse rate, and oral temperature performed after subject is in seated or in a recumbent position ≥ 3 minutes) including weight
- Perform physical examination
- Perform breast examination
- Perform gynecological examination
- Measure vaginal pH
- Obtain vaginal smear for assessment of maturation index
- Assess VHI
- Assess VuHI
- Obtain vulvo-vaginal imaging (optional)
- Perform TVU and measure endometrial thickness. Capture images to be sent to the central reader
- Obtain blood samples for safety laboratory tests, hormone levels and serum markers of bone metabolism
- Obtain urine sample for urinalysis and urinary marker of bone metabolism
- Assess study medication returned and assess compliance with study medication
- Assess eDiary compliance. For subjects who received a device, it should be collected

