6.3 Study Day and Analysis Windows

Day 1 is the initial dose date for subjects. Previous day to Day 1 is expressed as Day -1, and days before Day -1 in Screening Period are expressed as Day -2, Day -3, ... , etc.

Allowance window for each of the scheduled visits is shown in Table 1.

Allowance window for diary data is shown in Table 2.

If more than one visit occurs during a visit window, the one closest to the target day will be assigned to the visit. If two visits are equidistant from the target day, the latter visit will be assigned to the visit for post-baseline values.

If a subject discontinues from the study, the data obtained at early termination visit will be treated as one visit data based on the allowance windows.

Table 1 Definition of Visit Window

Scheduled Visit	Target Day	Window (Days)
Visit 1	Day -28	≤ Day -1
Visit 2 (Day 1)	Day 1(Randomization)	Day 1
Visit 3 (Week 4)	Day 29	Day 16 to Day 43
Visit 4 (Week 8)	Day 57	Day 44 to Day 71
Visit 5 (Week 12)	Day 85	Day 72 to Day 99
Early termination	Last dosing date	+ 14

Table 2 Definition of Diary Data Window

Week	Daily Data	Weekly Data (Target Day)
Week 1	Day 1 to Day 7	Day 4 to Day 10 (Day 7)
Week 2	Day 8 to Day 14	Day 11 to Day 17 (Day 14)
Week 3	Day 15 to Day 21	Day 18 to Day 24 (Day 21)
Week 4	Day 22 to Day 28	Day 25 to Day 31 (Day 28)
Week 5	Day 29 to Day 35	Day 32 to Day 38 (Day 35)

Week	Daily Data	Weekly Data (Target Day)
Week 6	Day 36 to Day 42	Day 39 to Day 45 (Day 42)
Week 7	Day 43 to Day 49	Day 46 to Day 52 (Day 49)
Week 8	Day 50 to Day 56	Day 53 to Day 59 (Day 56)
Week 9	Day 57 to Day 63	Day 60 to Day 66 (Day 63)
Week 10	Day 64 to Day 70	Day 67 to Day 73 (Day 70)
Week 11	Day 71 to Day 77	Day 74 to Day 80 (Day 77)
Week 12	Day 78 to Day 84	Day 81 to Day 87 (Day 84)

Assessments that occur more than 14 days after the last dose of study medication will be excluded from the above visit windows.

The baseline is defined as the last value that is observed prior to the first dose of study medication. For a variable that is planned to be observed at screening and randomization, the data at randomization will be used as baseline. For such variable, if the data at randomization is missing for a subject, the data observed at screening will be used as baseline.

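### SAP 10.3 item 3 gives conflicting rules on which samples count for the pre-defined laboratory limits; one of them leaves out early-termination blood drawn after the last dose

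*SAP*

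**What the plan says.** SAP 10.3 schedules safety laboratory tests at two pre-dose points (screening and randomization) and two later ones (Week 12, and ET for women who leave before Visit 5). The Schedule of Time and Events agrees and shows none at Week 4 or Week 8. Protocol 8.5 confirms the ET draw: "Obtain blood samples for safety laboratory tests, hormone levels and serum markers of bone metabolism".

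Items 1 and 2 of SAP 10.3 summarize laboratory values at baseline and Week 12. Item 3 covers the Appendix 3 limits in three steps:

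- The "proportion of subjects who meet the predefined limits at any timepoints will be calculated".
- Results later than Visit 5 are left out of this count.
- A closing sentence then names the sample to be used: "The analysis will be applied to data taken at the last timepoint before stopping dosing until Visit 5".

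Item 3 gives no denominator.

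The general rule in SAP 6.3 keeps ET results: "the data obtained at early termination visit will be treated as one visit data based on the allowance windows". Its cut-off is "Assessments that occur more than 14 days after the last dose of study medication will be excluded from the above visit windows". Table 1 in that section sets the ET target at the last dosing date, with an allowance of 14 days after it. SAP 10 takes the last non-missing pre-dose value as the safety baseline.

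**The concern.** The first and last sentences of item 3 select different samples, and nothing ranks them. The last sentence begins by referring to the analysis just described, so a programmer could reasonably apply it as a restriction on the any-time count.

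With no scheduled sample between randomization and Week 12 or ET, that restriction has an odd result. For many early stoppers, the last sample before dosing ended would be the one taken before dosing began. Their ET result, which was collected for safety, would be ignored in the one table designed to flag marked laboratory changes. A restriction of this kind also conflicts with SAP 6.3, which allows samples up to 14 days after the last dose.

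**Working it through.** The plan states no figure for this table, so there is nothing to reproduce. The check sets the rules side by side, counts the criteria affected, and then gives a sized illustration.

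**1. Which sample is used.** Take a woman who stops before Visit 5, whose ET blood is drawn 1 to 14 days after her last dose, and who has no unscheduled on-treatment sample.

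- Any-time rule with SAP 6.3: the ET sample counts.
- Last sentence taken as governing: the ET sample is too late. The latest eligible sample is from randomization, which is her baseline, so her change is zero.

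**2. Which criteria are affected (SAP Appendix 3).**

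- Need a difference from baseline: hemoglobin 1, WBC 2, neutrophils 2, lymphocytes 2, platelets 2, BUN 1, creatinine 1, total bilirubin 1, alkaline phosphatase 1, potassium 2, sodium 2, calcium 2. Sum = 19.
- Absolute value: AST 4, ALT 4, AST or ALT 4, AST/ALT combined with bilirubin 1, CK 1. Sum = 14.
- Total 19 + 14 = 33.

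On a baseline sample the 19 cannot be met. Of the 14, 13 need AST or ALT above at least 3 x ULN. Exclusion criterion 24 (Protocol 4.3) bars women above that level at screening, so a randomization sample is very unlikely to meet them.

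**3. Whether another laboratory summary picks up the ET sample.** In SAP Table 1 the Week 12 window runs from Day 72 to Day 99. An ET sample before Day 72 falls outside it and so enters no Week 12 figure in items 1 and 2. Item 3 is the only laboratory summary in SAP 10.3 that can capture it.

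**4. Size, on assumed rates.** The documents give neither a dropout rate nor limit rates. Let d be the share stopping early, p the limit rate in completers and r the rate in stoppers. Assume every stopper is in the situation of step 1 and every completer is counted.

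- Incidence with ET counted: (1-d)p + dr
- Incidence with ET left out, stoppers kept in the denominator: (1-d)p
- Share of affected women lost: dr / [(1-d)p + dr]
- Incidence if stoppers leave the denominator: p

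With p = 2%:

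| d | r | ET counted | ET left out | Affected women lost | Shortfall if stoppers leave the denominator |
|---|---|---|---|---|---|
| 5% | 2% | 2.0% | 1.9% | 5% | 0% |
| 5% | 6% | 2.2% | 1.9% | 14% | 9% |
| 5% | 10% | 2.4% | 1.9% | 21% | 17% |
| 10% | 2% | 2.0% | 1.8% | 10% | 0% |
| 10% | 6% | 2.4% | 1.8% | 25% | 17% |
| 10% | 10% | 2.8% | 1.8% | 36% | 29% |
| 15% | 2% | 2.0% | 1.7% | 15% | 0% |
| 15% | 6% | 2.6% | 1.7% | 35% | 23% |
| 15% | 10% | 3.2% | 1.7% | 47% | 38% |

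Example, d = 10% and r = 6%: 0.90 x 2% + 0.10 x 6% = 1.8% + 0.6% = 2.4%; lost 0.6/2.4 = 25%; shortfall with the reduced denominator 1 - 2.0/2.4 = 17%.

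**5. Effect on the difference between arms.** With stoppers kept in the denominator, leaving out ET removes d x r (ospemifene) minus d x r (placebo) from the ospemifene-minus-placebo difference. With d = 10% in both arms, r = 10% on ospemifene and 2% on placebo, that is 1.0% - 0.2% = +0.8 percentage points. With the two rates swapped it is -0.8. The sign is not fixed.

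**The case against.** The best defence is that item 3 describes two displays, one for any timepoint and one for the last on-treatment value. SAP 10.3 names ET as a sampling point and SAP 6.3 keeps ET data, so a careful programmer might count it. This is plausible, and it is why the point is an inconsistency and not a settled rule that discards ET data. But the SAP does not say that there are two displays, and even a deliberate last-value display would rest on a pre-dose sample for the women in question.

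Stronger readings are tempting, and the documents do not support them:

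- *That an early stopper can never meet a change-based limit.* Protocol 8 allows unscheduled visits, and an ET sample on its Table 1 target day falls on a dosing day. Either could supply an eligible value.
- *That women who stop because of a laboratory signal are the ones lost.* With no scheduled on-treatment draw before Week 12 or ET, such a signal implies an unscheduled sample before the stop, and that sample could count. The exposed group is women who stop for other reasons, including symptoms, and are sampled only afterwards.
- *That completers lose their Week 12 sample as well.* Protocol 7.9 caps exposure at 12 weeks (Day 84), and the Visit 5 target is Day 85. But SAP 8.2 runs a completer's dosing period through the date of Visit 5, so her sample falls within it.
- *That the between-arm difference is understated.* Step 5 of the working shows that it can move either way, and no document suggests that stopping differs by arm.

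It is also fair to say that the size is wholly assumed and depends on an unstated denominator. Other routes exist too: by-subject listings (Protocol 9.1), the Liver Event Form (Protocol 7.6.11.7), and the tables of chemistry-related events and events leading to withdrawal (SAP 10.1). These limit the harm. They do not replace a count against fixed numerical limits.

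**Conclusion.** The point holds as an inconsistency within SAP 10.3 item 3, and between it and SAP 6.3, on which samples count. If the last sentence governs, the Appendix 3 table leaves out ET blood drawn after the last dose. For women with no unscheduled on-treatment sample, that disables 19 of 33 criteria outright and 13 more in practice.

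At 10% early stopping and a 2% rate in completers, the loss runs from about 10% of affected women (equal rates) to 25-36% (stopper rates of 6-10%). In the latter case the shortfall in incidence is 17-29% if stoppers leave the denominator. These figures are illustrations, because no rate in them comes from the documents. The primary efficacy analysis is not touched. The correction is still worth making before the blind is broken, since a descriptive safety table should not depend on which sentence the programmer follows.

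**What to change.** Replace the last sentence of item 3 with wording to this effect:

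- **Samples.** The main analysis counts a woman as meeting a limit if any post-baseline value meets it, scheduled or unscheduled, up to Visit 5. This includes an ET sample taken no more than 14 days after the last dose, as in SAP 6.3.
- **Denominator.** Women with a baseline value and at least one such post-baseline value for the analyte.
- **Last-value display, if wanted.** Label it as additional and define it as the last post-baseline value up to Visit 5 and within 14 days after the last dose, so that a pre-dose sample can never stand in for it.

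The cost is a few lines of SAP text and the matching selection rule in the program. No new data are needed, because Protocol 8.5 already collects the ET blood.
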